### 3. Identify change patterns by predictors.

Analysis of temporal/cohort changes in the variables across all the data collection (tranches  $\underline{2}$  and  $\underline{3}$ ). The methodology for this exploration is all within the MLM described above, and the extension of the MLM with LPA and NNA.

# 4. Evaluation of the care types (inpatient, day hospital, and outpatient).

As with diversity of change, this aim will be explored largely through baseline/termination change broken down by types of care and, if numbers are large enough (to be explored by simulation) also by MLM and survival analysis with type of care as predictor (tranches  $\underline{1}$ ,  $\underline{2}$  and  $\underline{3}$ ).

However, this is clearly not a simple predictor/response relationship and there are two main complicating issues: that participants can have multiple trajectories through types of care, and that the types of care offered will reflect clinical need/severity and, probably to a lesser extent, demographic issues including age, occupation and carer responsibilities.

We expect that only a minority of the participants will receive only a single type of care as almost all who start in inpatient or day hospital care will progress to a less intense type of care and inpatient care unless they are very late recruits (and even then, transitions will be seen in the second, follow-up, phase of data collection). Inpatient care will often be succeeded by day hospital care and that in turn by outpatient care. A further complication is that a subset of participants will have "upward" as well as "downward" transitions and the diversity of trajectories across types of care will only permit robust MLM if only the major and simplest trajectories are analysed treating levels of care as time dependent covariates. For this reason, analyses will be only of the "simple transitions" but presented with clear caveats about the dangers of extrapolating overconfidently to all future clients starting in any of the three care types without taking the real complexities of transitions into account.

The second challenge, that types of care offered will undoubtedly be affected by severity (hence probably strongly correlated with scores on measures) and by some aspects of demography, can only really be explored in terms of associations with scores and with

demographics at baseline by type of care, and for the categories of later care type transitions.

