# 3. Primary objective: Effectiveness of ITAMITED as it is applied routinely in its natural context.

We will analyse effectiveness with three complementary analyses performed for data/analysis tranches 2 and 3.

(a) Baseline/termination change. This is has been the traditional focus of many existing explorations of effectiveness of treatment. We will report both mean change and also effect sizes reporting Cohen's d2 and dz (Cohen, 1988) (the ratio of mean change to baseline SD and the ratio of mean change to SD of change respectively) and report these with bootstrap CIs. As well as reporting the global aggregate mean shifts with bootstrap 95% CI for each score. We will report the regression of termination scores on baseline scores and the distributions of change scores.

We will explore the impact of baseline variables: gender, age, diagnosis, demographic

variables, medication use and service on change. These predictor effects will be explored entering them as predictors of termination scores/values in ANOVA models with attention paid to the almost certain violation of assumptions of the ANOVA and exploration of mitigation of those violations. As gender and age are such crucial variables in Eating Disorders (Eds) the effects of entering these as predictors (or analysing separately be gender) on effects of other variables will be reported.

To address individual change we will report the Jacobson plot of termination against baseline scores for all scores and report the RCSC breakdown of change on each measure where it is possible to define the CSC and RCI.

(b) Multilevel models (MLM) of rates of change. MLM allows analysis of change slopes across diverse durations of therapy/ascertainment and the method handles the nonindependence of observations arising from the repeated measures within participant appropriately. These analyses can give a much more nuanced picture of change than baseline/termination analyses while allowing exploration of the effects of the same predictors and covariates analysed in (a). As for (a), durations of therapy are not directly reflected in the analyses though in contrast to (a), all data across all durations of data collection are used rather than just the first and last values.

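### With care type as a time-dependent covariate, the planned multilevel model can show roughly 0.4 to 1 baseline SD between identical care types, and the plan has no safeguard in the model

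*SAP*

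**What the plan says.** All of this is in the SAP, Secondary objectives, 4 (Evaluation of the care types), unless stated.

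- **Main analysis:** "this aim will be explored largely through baseline/termination change broken down by types of care".
- **Second analysis, conditional:** "if numbers are large enough (to be explored by simulation) also by MLM and survival analysis with type of care as predictor".
- **Form of the multilevel model (MLM):** only the major, simplest paths are analysed, "treating levels of care as time dependent covariates".
- **Direction of moves:** "almost all who start in inpatient or day hospital care will progress to a less intense type of care".
- **Dependence on severity:** "types of care offered will undoubtedly be affected by severity (hence probably strongly correlated with scores on measures". The plan adds that this "can only really be explored in terms of associations with scores and with" demographic variables, at baseline and by category of later transition.
- **Promised caveat:** results are to be "presented with clear caveats about the dangers of extrapolating overconfidently to all future clients starting in any of the three care types".
- **What the MLM is credited with (Primary objective, part b):** "the method handles the nonindependence of observations arising from the repeated measures within participant appropriately".

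The plan does not say which care type a score taken at a move is coded to, whether baseline or earlier scores enter the care-type model, or which random effects are used.

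**The concern.** The model takes care type as given and attributes differences in score to it. By the plan's own account the dependence also runs the other way, because severity decides the care. This enters in two ways.

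1. **Starting care.** More severe participants start in more intense care. Their high baseline score then counts as an outcome under that care.
2. **Moves.** A step down tends to follow improvement. If the score that prompted the move is coded to the new care, or if current unmeasured severity prompts it, the new care is credited with improvement that came before it.

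Both push the same way: inpatient care looks worse and outpatient care better, even if the types do not differ. Handling dependence among repeated measures is a different matter and does not address this. Nor does the restriction to simple transitions, which keeps the downward moves through which improvement selects the next care type. At stake is the model-based part of the answer to objective 4.

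**Working it through.** The plan gives no sample size, effect or strength of dependence for this analysis, so there is no figure to reproduce. The check is in two parts.

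**1. When the plain MLM is protected.** Write the score as y(t) = intercept + slope × t + error, with care C(t).

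- If C(t) depends only on scores observed before t, the probability of the care decision factors out of the likelihood. A model with the correct random effects is then not biased by the moves.
- This fails if C(t) depends on y(t) itself, or on current severity that earlier scores do not capture.
- It also fails at the start if C(0) depends on y(0) or on severity and y(0) is kept as an outcome under C(0).
- It weakens if the random effects are too simple, for example a random intercept alone.

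**2. Size, by simulation with no care-type effect.** All inputs are assumed: 300 participants, 8 occasions, 100 runs per scenario, a common downward trend, downward moves only, log-odds of moving −1.5 per score unit.

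- Independent errors: intercept SD 0.7 and error SD 0.6, so baseline SD = √(0.7² + 0.6²) = 0.92.
- Autocorrelated errors (0.7): component SDs 0.6, 0.6 and 0.4, so baseline SD = √(0.6² + 0.6² + 0.4²) = 0.94.

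Entries are the spurious inpatient-minus-outpatient difference in score units, with rejection at 0.05. RI = random intercept; RIS = random intercept and slope. Adjusted = RIS with each score coded to the care decided before it, and the baseline score (and its product with time) as covariate, not outcome.

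| Starting care | Move triggered by | Plain RI | Plain RIS | Adjusted |
|---|---|---|---|---|
| Random | Chance (control) | 0.00 (5%) | 0.00 (6%) | −0.01 (7%) |
| Unrelated to severity | Previous score | +0.07 to +0.20 (22–93%) | 0.00 to +0.06 (4–15%) | 0.00 to +0.03 (3–9%) |
| Random | Same-visit score, coded to new care | +0.45 to +0.50 (100%) | +0.46 to +0.55 (100%) | −0.01 to +0.01 (8–9%) |
| Random | Current latent severity | +0.42 (100%) | +0.42 (100%) | +0.09 (26%) |
| By severity | Previous score | +0.46 to +0.59 (100%) | +0.46 to +0.50 (100%) | +0.01 to +0.03 (6–8%) |
| By severity | Same-visit score, coded to new care | +0.85 to +0.95 (100%) | +0.87 to +0.95 (100%) | 0.00 to +0.02 (3–6%) |
| By severity | Current latent severity | +0.83 (100%) | +0.80 (100%) | +0.21 (76%) |

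In baseline SDs (simulated value for each scenario), the biased RIS rows run from 0.415/0.94 = 0.44 to 0.949/0.93 = 1.02. After adjustment the largest value is 0.033/0.93 = 0.04 SD when observed scores drive care. When latent severity drives care, 0.089/0.94 = 0.09 and 0.207/0.93 = 0.22 SD remain. With 100 runs, the Monte Carlo standard error of a 5% rejection rate is √(0.05 × 0.95/100) = 2.2 points, so 3–9% is compatible with 5%.

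**Other simulations, also with no care-type effect.**

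- 8 occasions, 40 runs, baseline SD 0.94, RIS. Severity-based start with observed-score moves: +0.58 (coded to the care before the move) and +0.93 (new care), that is 0.62 and 0.99 SD. Random start with observed-score moves and prior-care coding: +0.01 (5%). Random start with latent severity: +0.15 to +0.22 (70–88%), or 0.16 to 0.23 SD, below the range in the heading.
- 8 occasions, 30 runs, some fits with convergence warnings. Severity-based start: +0.59 to +0.91 score units under either coding (100%).
- 13 monthly scores, 24 runs, same-occasion coding: outpatient −0.61 and inpatient +0.60 SD against day hospital. With the preceding month's care: −0.18 to −0.27 and +0.30 to +0.38.

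**Move-versus-stay comparison.** The next score is regressed on moving or staying within current care type, given the current score and time. With observed-score triggers and 13 months (200 runs), bias was about 0.01 SD or less and rejection 4–9%. With true severity as the trigger, bias was −0.21 to −0.36 SD and rejection 87–100%.

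A simple inverse-probability-weighted model left +0.03 to +0.16 score units and is not relied on.

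**The case against.** The other side has four fair points.

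- **Status.** The MLM is conditional on numbers and comes second to baseline/termination change. Under General statistical approach the SAP calls its methods exploratory and descriptive, and accepts that associations will have several explanations.
- **Concession.** The plan says this is not a simple predictor/response relationship and names severity as a driver, including at later transitions. It nowhere claims that the coefficient is a causal effect.
- **Conditional size.** The plan fixes neither the coding nor the random effects, and in one set of conditions the bias is near zero.
- **Partial remedy.** Care is said to reflect clinical need, not a questionnaire score alone, so adjusting for scores may leave bias.

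All four stand as limits on the point, but they do not remove it. The acknowledgement changes nothing in the model, and the promised caveat concerns extrapolation, not scores driving moves. The harmless conditions include starting care unrelated to severity, which conflicts with the plan's own statement.

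A reader might infer that the time-dependent covariate must make identical care types look strongly different, that feedback during treatment is the whole cause, or that adjusting for severity at entry cannot help. Neither the plan nor the simulations support that. The strong bias depends on choices the plan leaves open or on how care is assigned, and much of it comes from severity-based starting care. Correct timing plus the baseline score removed nearly all of it when observed scores drove care.

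**Conclusion.** The concern holds in a limited form. The plan enters into a model of scores a covariate that it says depends on severity and is probably strongly correlated with those scores. It gives no timing rule and no adjustment, and it treats description as the only option. Under its own premise that severity affects the care offered, the plain MLM gave about 0.5 to 1 SD between identical care types in the main simulation. Across most scenarios the range is roughly 0.4 to 1 SD, with individual results outside it as shown. These sizes rest on assumed sample size, trend, trigger strength and error structure, since the plan supplies none. The direction was the same in every simulation that showed appreciable bias in the plain model.

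This is not an error in the main analysis of objective 4, which is baseline/termination change. It is a correctable weakness in a secondary, conditional analysis, and should be fixed before the model is used to compare care types.

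**What to change.** In Secondary objectives, 4, for any model-based comparison of care types:

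1. Code each score to the care decided before it.
2. Condition on the score preceding the care decision, in one of two ways:
   - **MLM:** use the baseline score and its product with time as covariates, not the baseline score as an outcome. Specify random intercepts and slopes.
   - **Move versus stay:** at each completion, among participants in the same care type, compare those who then move with those who stay. Take the next score as outcome. Adjust for current and earlier scores, time, and the demographic drivers the section names (age, occupation, carer responsibilities). Pool occasions with participant-clustered intervals.
3. Report the plain time-dependent MLM only as a description of scores seen in each care type, with a caveat that moves follow scores.
4. State that the adjusted comparison removes the bias only as far as measured scores capture the severity that drives care. About 0.1 to 0.4 SD remained in simulations where they did not.

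The cost is SAP wording and re-use of data already planned. The move-versus-stay comparison answers a narrower question, short-term change after a move. It uses only occasions when a move was possible, so intervals will be wider.

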### 5. Describe the main challenges implementing PBE.

We believe this DAP underlines many of the challenges of *analysing* PBE data. One particular challenge, affecting all the above analyses, is that of non-participation. The relatively small issue of missed items has been noted above but other missing data is likely to be far more important. For all the analyses described above we will describe initial refusals and withdrawals and will also report data loss by exclusions and administrative errors and explore how these may have affected data.

Particular attention will be paid to cohort/time changes in missingness, and to differences between centres. It is recognised that recruitment since the coronavirus (CV-19) pandemic will have been affected and this will be studied specifically against the timing of the public health measures imposed and how ITA reacted made operational changes. These analyses are expected to be conducted in all the three tranches.

Given that none of the missingness is likely to be truly "Missing at Random" (MAR) let alone "Missing Completely at Random" (MCAR) we believe that the sophisticated imputation methods, such as Multiple Imputation by Chained Equations (MICE), which are powerful and unbiased for MCAR, and strong for some MAR models, may have limited or no advantages over crude substitutions (means across all participants for the missing data, or means for that participant) or simple deletions (listwise/casewise) all of which can introduce strong biases into analyses. We will use methods, in the light of the observed patterns of missingness, and report their impacts on analyses as robustness checks rather than as solutions for missingness.

In addition to these data analytic challenges, many of which are far more severe than for analysis of trial data, and are consequently less explored, there are simple challenges of implementing PBE data collection without substantial research funding. We will describe qualitatively, the challenges and how we sought to manage and mitigate them, where possible. Where, as with missingness, quantitative data throw light on success or failure of mitigation, these data will be reported.

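### The care-type evaluation is limited to simple transitions, a set fixed by the path followed after entry, and the SAP does not say which analyses the limit covers or plan to show change in those set aside.

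*SAP*

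**What the plan says.** All of the care-type text is in the SAP, Secondary objectives, section 4 (Evaluation of the care types).

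- **Main analysis.** The section says that "this aim will be explored largely through baseline/termination change broken down by types of care".
- **Conditional analyses.** If numbers are large enough, which is to be explored by simulation, care types are evaluated "also by MLM and survival analysis with type of care as predictor".
- **Reason for a limit.** Some participants move up as well as down between levels of care. The SAP says this diversity "will only permit robust MLM if only the major and simplest trajectories are analysed treating levels of care as time dependent covariates".
- **The limit.** The next sentence reads: "For this reason, analyses will be only of the 'simple transitions' but presented with clear caveats". The caveats concern extrapolation to all future clients who start in any of the three care types.
- **Confounding.** The section states that "types of care offered will undoubtedly be affected by severity (hence probably strongly correlated with scores on measures". It says this can only be explored through associations with scores and with "demographics at baseline by type of care, and for the categories of later care type transitions".

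Two other sections bear on the point. Section 3 (Primary objective), part (a), plans to "report the regression of termination scores on baseline scores and the distributions of change scores", with no limit by care path. Secondary objective 5 says of all the analyses that the team "will also report data loss by exclusions and administrative errors and explore how these may have affected data".

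**The concern.** Whether a participant's transitions count as simple is settled only after treatment has begun. A move back to more intensive care may well follow a poor course, and the SAP expects the care offered to depend on severity. Keeping participants by path can therefore mean keeping them by outcome. Mean change by care type would then describe those whose path stayed simple, while a reader might take it as change in everyone who entered that level of care.

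The wording leaves open how much of the objective is affected. The reason is about the MLM, but the conclusion speaks of analyses without qualification, and the objective has three kinds. One analyst could restrict only the MLM and another could restrict all three. Both would be following the text, and their main results could differ.

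The SAP rests its defence against p-value hunting on a clear line between planned and emergent analyses (General statistical approach, section 1). An analysis set that can still be defined after change data have been seen weakens that line.

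**Working it through.** **1. Is there a figure to reproduce?** No. The SAP gives no share of participants with complex paths and no expected difference in change. The first check is textual.

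**2. Scope of the limit.**

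| Analysis under objective 4 | Status in the SAP | Covered by the limit? |
|---|---|---|
| Baseline/termination change by care type | main analysis | not stated |
| MLM with care type | only if numbers allow | yes, since the reason given is about the MLM |
| Survival analysis with care type | only if numbers allow | not stated |

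**3. What is promised about those set aside.**

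- Baseline associations by transition category (section 4): these describe starting points and commit to no result on change.
- Caveats (section 4): these warn about extrapolation and give no size.
- Data loss by exclusions (secondary objective 5): this is a general promise, made under non-participation and missing data, and does not mention care path.
- Aggregate change (section 3): these participants are included, but results are not split by path.

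None of the four commits to showing change in the participants set aside.

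**4. How large could the effect be?** Every input here is an assumption. Let p be the share set aside, K the mean change in those kept and S the mean change in those set aside. The mean in all participants is (1 - p)K + pS, so

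K - mean(all) = p x (K - S).

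| p | K - S = -0.5 SD | K - S = 0 | K - S = +1.0 SD |
|---|---|---|---|
| 5% | -0.025 | 0 | +0.05 |
| 10% | -0.05 | 0 | +0.10 |
| 25% | -0.125 | 0 | +0.25 |

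**5. Would the planned baseline associations reveal it?** This is a simulation on assumed values, with 2,000,000 draws. Baseline b is normal with mean 0 and SD 1. Change (positive = improvement) is 0.6 + 0.5b + e, where e has variance 0.75. The variance of change is then 0.25 + 0.75 = 1, and the true mean is 0.60 SD. The probability of being set aside is logistic(a + L), with a chosen to give p = 5%, 10% or 25%.

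| What drives being set aside | Mean change in kept (5%, 10%, 25%) | After regression on baseline | Baseline of those set aside compared with kept |
|---|---|---|---|
| Nothing (L = 0) | 0.60, 0.60, 0.60 | 0.60 throughout | same |
| Baseline severity (L = b) | 0.58, 0.56, 0.49 | 0.60 throughout | about 0.94, 0.91, 0.85 SD higher |
| Change not explained by baseline (L = -e) | 0.64, 0.67, 0.77 | 0.64, 0.67, 0.77 | same |
| Change itself (L = -change) | 0.65, 0.69, 0.81 | about 0.64, 0.67, 0.77 | about 0.4 to 0.5 SD lower |

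If selection follows baseline severity alone, the kept mean is too low, and regression on baseline restores it. If it follows change not explained by baseline, the kept mean is too high, regression does not help, and the baseline comparison shows nothing. If it follows change itself, the baseline comparison shows a difference, but regression removes only part of the shift. So baseline associations would show a difference in two of the three selective cases, and in none of the three would they measure how change differs. A table of change in those set aside would.

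**The case against.** The strongest reply is about scope. The limit follows directly on a sentence about MLM feasibility, so the natural reading confines it to the MLM, and that model runs only if numbers allow. On that reading the main care-type analysis is untouched. This stands. A reader might infer that the SAP restricts its baseline/termination analysis. The text leaves that open but does not say it.

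A second reply is that those set aside are not ignored. Baseline associations by transition category, a general report of exclusions and explicit caveats are all planned, and the primary analyses state no restriction by path. It can also be argued that the words at baseline attach only to demographics, so that later scores by transition category are not clearly excluded. This stands in part. It would be wrong to infer that nothing is reported on these participants or that they drop out of the effectiveness result. But even the wider parsing commits to no result on change.

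Third, the illustrated shifts are assumed. In the scenario closest to the mechanism the SAP names, severity, the kept mean is too low and regression on baseline corrects it. This stands too: neither an upward bias nor any particular size can be claimed for this study.

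Fourth, the SAP describes itself as a shortened version of a larger document that accompanies a protocol paper, so a list of qualifying sequences may exist elsewhere. For that reason the missing definition alone would not be a finding. What remains is the rule that the SAP does state, selection on a path known only after entry, with no planned view of change in those it removes.

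Finally, change on the major pathways is a legitimate descriptive quantity. It needs to be labelled as such and shown beside the result in all participants.

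**Conclusion.** The concern holds in a limited form. The SAP states a rule that selects participants on their path after entry, its own account makes that path plausibly related to outcome, and it does not plan to show change in those set aside. Under the natural reading this affects only the conditional MLM. Under the wider reading, which the wording permits, it also affects the main care-type analysis and the survival analysis.

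The size and direction of any shift cannot be derived from the SAP. The range of -0.125 to +0.25 SD at 25% set aside illustrates the arithmetic on assumed inputs, and the shift is zero if the two groups change equally. The documents do not support a statement that the care-type results will be biased in a given direction.

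Severity is low (consider). The objective is secondary, the SAP calls its methods exploratory and descriptive, and the primary analyses carry no such limit.

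**What to change.** In Secondary objectives, section 4:

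1. State that the limit to simple transitions applies to the MLM only, and list the qualifying sequences of care types before tranche 2 change data are examined.
2. Run baseline/termination change on all participants by care type at entry, adjusted for baseline score and the predictors named in section 3(a): gender, age, diagnosis, demographic variables, medication use and service. Say that any survival analysis by care type also uses all participants.
3. Report, by entry care type, the number and change of participants the MLM sets aside, next to the baseline associations already planned.

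The cost is a few sentences of wording, one adjusted model per measure and one table, all from scores and care types that the study already holds. The downside is that an estimate by entry care type describes the whole pathway that began at that level and cannot isolate the level itself. Confounding by unmeasured severity also remains, and the report should say so.
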